6.3.2.2 Growth chart for height by age and sex

Similar to the BMI growth chart, the height growth chart (CDC, 2009) provides the L, M, and S parameters by age and sex, where the age is provided in months at the half-month point.

In the Growth Chart for Height, the L, M, and S parameters for each age in years were mapped to the chart values corresponding to the half-year time point for that year, with respect to sex.

Table 6–7: Growth Chart for Height¹ (cm) by Age and Sex

Sex	Age (years)	Month in the chart	L	M	S
Male	12	150.5	0.531951655	152.6623878	0.050273285
Male	13	162.5	1.232768816	160.3493168	0.049926861
Male	14	174.5	2.016781776	167.4641466	0.047506783
Male	15	186.5	2.2253265	172.1562865	0.044362674
Male	16	198.5	1.927320937	174.6309856	0.042107465
Male	17	210.5	1.543252982	175.8359757	0.040938463
Female	12	150.5	1.358162799	154.755501	0.046198356
Female	13	162.5	1.076970655	159.2074654	0.042114211
Female	14	174.5	0.902452436	161.3267744	0.040409354
Female	15	186.5	0.913397733	162.2908474	0.039913066
Female	16	198.5	0.971038162	162.7718741	0.03976685
Female	17	210.5	1.025142554	163.0401953	0.039706971

¹ Centers for Disease Control and Prevention (2009). https://www.cdc.gov/growthcharts/percentile_data_files.htm

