5.6.3.6.2 Growth assessment

Descriptive statistics for height and weight change from baseline will be reported by weight-categorized dose group over time. Growth percentiles will be calculated for height, weight, and body mass index (BMI) at Week 16, Week 64, and Week 124. A shift table of the number and percentage of participants falling in each percentile category from baseline to these post-baseline visits will be presented by weight-categorized dose group. The percentile categories are listed below.

- Height (percentile):
 - $<5^{\text{th}}$
 - $\geq 5^{\text{th}}$ to $<25^{\text{th}}$
 - $\geq 25^{\text{th}}$ to $<50^{\text{th}}$
 - $\geq 50^{\text{th}}$ to $<75^{\text{th}}$
 - $\geq 75^{\text{th}}$ to $<95^{\text{th}}$
 - ≥ 95
- Weight (percentile): the same percentile categories as height
- BMI (percentile):
 - $<5^{\text{th}}$ (underweight)
 - $\geq 5^{\text{th}}$ to $<85^{\text{th}}$ (normal or healthy weight)
 - $\geq 85^{\text{th}}$ to $<90^{\text{th}}$ (overweight)
 - $\geq 90^{\text{th}}$ to $<95^{\text{th}}$ (overweight)
 - $\geq 95^{\text{th}}$ to $<97^{\text{th}}$ (obese)
 - $\geq 97^{\text{th}}$ (obese)

Height and weight percentile reference levels are provided in Section 6.3.2.

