6.1.9.2 Marked abnormality criteria for vital signs

The marked abnormality criteria for blood pressure are provided in the table below:

Table 6–5: Definitions of Markedly Abnormal Vital Signs

Parameter (unit)	Age group	Markedly Abnormal Low	Markedly Abnormal High
Systolic blood pressure (mmHg)	≤17	<90 or a decrease from Baseline of ≥30%	>5 above the 99 th percentile
	>17	<90 or a decrease from Baseline of ≥30%	>160 or an increase from Baseline of ≥30%
Diastolic blood pressure (mmHg)	≤17	<50 or decrease of ≥20% from Baseline	>5 above the 99 th percentile
	>17	<50 or decrease of ≥20% from Baseline	>105

The values of the 99th percentile of systolic and diastolic blood pressure values, by age, sex and height percentile are provided in Section 6.3.3 for participants aged 17 or less.

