6.3.1 Derivation of percentiles from LMS parameters

The L, M, and S parameters from growth charts for BMI, height, and weight, by age and sex, are provided in Section 6.3.2.

Deriving the percentile value of a given measurement, for a given participant is done in 3 steps (Cole, 1990):

1. From the growth chart of the measurement of interest (BMI, height, or weight), identify the L, M, and S parameters corresponding to the participant sex and age (at the time of the measurement).
2. Calculate the z-score for the measurement using the following formula:

$$z = \frac{\left[\left(\frac{X}{M}\right)^L - 1\right]}{L \times S}$$

Where X is the measurement value and L, M, and S are the parameters identified in step 1.

3. The calculated z-score is then converted to the percentile value using the cumulative distribution function from the standard normal distribution.

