6.3.2 Growth charts

6.3.2.1 Growth chart for BMI by age and sex

The BMI growth chart (CDC, 2000) provides the L, M, and S parameters by age and sex, where the age is provided in months at the half-month point. For example, 78.5 months represents the interval [78.0, 79).

In this study, age is recorded in years at each visit where the weight and height are recorded. In the BMI growth chart, the L, M, and S parameters for each age in years were mapped to the chart values corresponding to the half-year time point for that year, with respect to sex. For example, LMS values for a 12 year-old correspond to the half-year timepoint of $12.5 \times 12 = 150$ months, that is the interval [150.0, 151.0) represented by 150.5 months in the chart.

Table 6–6: Growth Chart for BMI¹ (kg/m²) by Age and Sex

Sex	Age (years)	Month in the chart	L	M	S
Male	12	150.5	-2.385858029	18.1387275	0.132990575
Male	13	162.5	-2.277017201	18.81201584	0.134879611
Male	14	174.5	-2.179425674	19.50672885	0.135308594
Male	15	186.5	-2.085574403	20.20858236	0.134718085
Male	16	198.5	-1.993150137	20.90294449	0.1336202
Male	17	210.5	-1.908831065	21.57417053	0.132584784
Female	12	150.5	-1.959520079	18.42002284	0.149783482
Female	13	162.5	-1.9610997	19.04811118	0.151176355
Female	14	174.5	-2.002014224	19.64746266	0.151009595
Female	15	186.5	-2.074459502	20.19980767	0.14984254
Female	16	198.5	-2.167044578	20.6891237	0.148349348
Female	17	210.5	-2.26238209	21.10163241	0.147323144

BMI=body mass index

¹ Centers for Disease Control and Prevention (2000). https://www.cdc.gov/growthcharts/percentile_data_files.htm

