6.3.3 Blood pressure 99th percentile values by age, sex and height percentile

The Blood Pressure 99th Percentile Values table presents the values of the 99th percentile of systolic and diastolic blood pressure, by sex, age, and height percentile, for participants with age ≤17 years. Height percentile is calculated as described in Section 6.3.1 and should be rounded up or down to the nearest percentile in Table 6–9.

Table 6–9: Blood Pressure 99th Percentile Values¹ (mmHg) by Age, Sex and Height Percentile.

Sex	Age (years)	Height percentile	99 th percentile Systolic BP (mmHg)	99 th percentile Diastolic BP (mmHg)
Male	12	5	126	86
Male	12	10	127	87
Male	12	25	129	88
Male	12	50	131	89
Male	12	75	133	90
Male	12	90	134	90
Male	12	95	135	91
Male	13	5	128	87
Male	13	10	130	87
Male	13	25	131	88
Male	13	50	133	89
Male	13	75	135	90
Male	13	90	136	91
Male	13	95	137	91
Male	14	5	131	87
Male	14	10	132	88
Male	14	25	134	89
Male	14	50	136	90
Male	14	75	138	91
Male	14	90	139	92
Male	14	95	140	92
Male	15	5	134	88

Table 6–9: Blood Pressure 99th Percentile Values¹ (mmHg) by Age, Sex and Height Percentile.

Sex	Age (years)	Height percentile	99 th percentile Systolic BP (mmHg)	99 th percentile Diastolic BP (mmHg)
Male	15	10	135	89
Male	15	25	136	90
Male	15	50	138	91
Male	15	75	140	92
Male	15	90	142	93
Male	15	95	142	93
Male	16	5	136	90
Male	16	10	137	90
Male	16	25	139	91
Male	16	50	141	92
Male	16	75	143	93
Male	16	90	144	94
Male	16	95	145	94
Male	17	5	139	92
Male	17	10	140	93
Male	17	25	141	93
Male	17	50	143	94
Male	17	75	145	95
Male	17	90	146	96
Male	17	95	147	97
Female	12	5	127	86
Female	12	10	127	86
Female	12	25	128	87
Female	12	50	130	88
Female	12	75	131	88
Female	12	90	132	89
Female	12	95	133	90
Female	13	5	128	87
Female	13	10	129	87

Table 6–9: Blood Pressure 99th Percentile Values¹ (mmHg) by Age, Sex and Height Percentile.

Sex	Age (years)	Height percentile	99 th percentile Systolic BP (mmHg)	99 th percentile Diastolic BP (mmHg)
Female	13	25	130	88
Female	13	50	132	89
Female	13	75	133	89
Female	13	90	134	90
Female	13	95	135	91
Female	14	5	130	88
Female	14	10	131	88
Female	14	25	132	89
Female	14	50	133	90
Female	14	75	135	90
Female	14	90	136	91
Female	14	95	136	92
Female	15	5	131	89
Female	15	10	132	89
Female	15	25	133	90
Female	15	50	134	91
Female	15	75	136	91
Female	15	90	137	92
Female	15	95	138	93
Female	16	5	132	90
Female	16	10	133	90
Female	16	25	134	90
Female	16	50	135	91
Female	16	75	137	92
Female	16	90	138	93
Female	16	95	139	93
Female	17	5	133	90

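### SAP 6.3.2 looks up growth percentiles by whole year of age, so children growing exactly on track change height band in the shift tables; a month-based or elapsed-time lookup removes most of this at low cost (minor)

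*SAP*

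**What the plan says.** SAP 6.3.1 converts a measurement X to a z-score with the LMS formula and then to a percentile. Its first step is to "identify the L, M, and S parameters corresponding to the participant sex and age (at the time of the measurement"). SAP 6.3.2.1 describes the source BMI chart as one "where the age is provided in months at the half-month point", and 6.3.2.2 says the same of the height chart.

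The SAP then coarsens this. Under 6.3.2.1, "In this study, age is recorded in years at each visit where the weight and height are recorded", and each whole year is given the chart row at its half-year point. The height section repeats the rule: "In the Growth Chart for Height, the L, M, and S parameters for each age in years were mapped to the chart values" for that year's midpoint. Tables 6-6 to 6-8 accordingly hold six rows per sex, for ages 12 to 17.

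The percentiles have two uses.

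- SAP 5.6.3.6.2 derives them at Weeks 16, 64 and 124: "A shift table of the number and percentage of participants falling in each percentile category from baseline to these post-baseline visits will be presented". The height and weight cut points are the 5th, 25th, 50th, 75th and 95th percentiles.
- SAP 6.3.3 uses the height percentile to choose a blood pressure limit: "Height percentile is calculated as described in Section 6.3.1 and should be rounded up or down to the nearest percentile in" Table 6-9.

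Separately, 5.6.3.6.2 reports raw change: "Descriptive statistics for height and weight change from baseline will be reported by weight-categorized dose group over time". That summary uses no percentile.

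**The concern.** At these ages the reference median moves quickly. Between the rows for 12 and 13 in Table 6-7 the boys' median rises by 160.35 − 152.66 = 7.69 cm. A boy aged 12.0 and a boy aged 12.9 are both scored against the median at 12.5, so the younger scores too low and the older too high. On the 13th birthday the reference jumps by a full year's growth. Two measurements 16 weeks apart can therefore fall in different bands with no change in the child's true standing.

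The shift tables are the only age- and sex-referenced summary of change in growth, and growth is a secondary safety endpoint. Someone reading them for a growth signal in a small adolescent study could not separate these moves from real ones.

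**Working it through.** The plan states no band-change rate, so there is no such figure to reproduce. Its one worked example is correct: 12.5 × 12 = 150 months, which is chart row 150.5.

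**Birthday step.** Inputs are the rows of Table 6-7, taken at the half-year. The median height on the birthday is taken as the midpoint of the two adjacent medians, and z = [(X/M)^L − 1]/(L × S). For a boy turning 13:

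- X = (152.66 + 160.35)/2 = 156.51 cm.
- Row 12: [(156.51/152.66)^0.532 − 1]/(0.532 × 0.0503) = +0.50, the 69th percentile.
- Row 13: [(156.51/160.35)^1.233 − 1]/(1.233 × 0.0499) = −0.48, the 32nd percentile.

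The same calculation for a child always at the median, as percentile the day before → the day after:

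| Birthday | Boy | Girl |
|---|---|---|
| 13 | 69 → 32 | 62 → 37 |
| 14 | 67 → 33 | 56 → 43 |
| 15 | 62 → 38 | 53 → 47 |
| 16 | 56 → 43 | 51 → 49 |
| 17 | 53 → 47 | 51 → 49 |

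**Band changes.** I simulated 400,000 children per sex. Each keeps one true z drawn from N(0,1). Starting age is uniform from 12.5 to 17.5 years less the elapsed time. True size comes from L, M and S interpolated linearly between the SAP's own rows. Both visits are then scored with the whole-year row and the bands compared, so every band change is false by construction.

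| Band change | Boys, Week 16 / 64 / 124 | Girls, Week 16 / 64 / 124 |
|---|---|---|
| Height | 31.6 / 26.0 / 35.2% | 13.0 / 10.0 / 14.4% |
| Weight | 25.0 / 20.8 / 27.9% | 14.5 / 11.8 / 16.1% |
| BMI | 5.3 / 4.4 / 5.9% | 4.2 / 3.4 / 4.6% |

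At Week 16 the height moves split 17% down and 15% up in boys, and 7% down and 6% up in girls. The mean false z-change is about −0.01 (SD 0.31 in boys, 0.15 in girls). Two-band jumps are 0.2% or less at every visit. False entry into the lowest height band (below the 5th) is about 1.4% of boys and 0.7% of girls.

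**Dependence on age.** Week 16 height-band change by age at entry, from a run over the full 12 to <18 range:

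| Entry age | 12 | 13 | 14 | 15 | 16 |
|---|---|---|---|---|---|
| Boys | 51% | 47% | 36% | 22% | 12% |
| Girls | 34% | 22% | 11% | 5% | 3% |

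Uniform ages over that full range, among those still under 18 at Week 16, give 30% of boys and 13% of girls. Age mixes skewed older or younger give 20 to 39% of boys and 6 to 19% of girls.

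**Blood pressure.** The systolic limit picked from Table 6-9 differs from the true-age limit in about 23% of boys and 9% of girls, but by at most 2 mmHg (diastolic at most 1 mmHg).

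**After the change.** Week 16 height-band change falls to about 2.6% of boys and 1.1% of girls with monthly rows. With Baseline whole-year age + 0.5 + elapsed time, interpolated and capped at the last row, it is 2.7 / 8.8 / 17.0% of boys and 1.8 / 5.9 / 10.5% of girls at Weeks 16 / 64 / 124.

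**The case against.** The strongest reply is that this is a declared approximation. SAP 6.3.2.1 says age is held in years and sets out the mid-year row as the way to apply 6.3.1, so the two sections do not conflict. The output is descriptive, the height and weight shift tables were added by the SAP (6.2), the protocol endpoint of raw change is intact, and both randomised doses are scored by the same rule. All of that stands, and it keeps the point minor. It does not make the approximation a good one at ages 12 to 14.

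Four stronger readings are tempting but not supported.

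- *That about a third of boys will be misclassified whatever the sample.* The rate depends on an age mix that neither document gives.
- *That much of the movement in the shift tables will be lookup noise.* The simulation sets true movement to zero, and the documents give no estimate of real movement, so the noise share is unknown.
- *That the 13th-birthday drop is typical.* It is the steepest in the table; by 17 a median boy moves only from the 53rd to the 47th percentile.
- *That participants aged 18 or over expose a serious gap.* With uniform entry over 12 to <18 and no dropout, the share is (weeks × 7/365.25)/6: about 5%, 20% and 40% at Weeks 16, 64 and 124. But SAP 5.1.1.7.4 analyses growth as observed without imputation, and SAP 5.1 displays the denominator when it differs from the analysis set. A participant with no chart row would simply leave a visible denominator. The blood pressure use is not exposed either, since the Table 6-9 values "are provided in Section 6.3.3 for participants aged 17 or less". Only a clarifying sentence is missing.

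**Conclusion.** The point holds as a cheap improvement of minor weight. With entry ages uniform over the chart span, the whole-year lookup by itself moves about 32% of on-track boys and 13% of on-track girls to another height band at Week 16. The range over other age mixes is 20 to 39% and 6 to 19%; the effect is largest at ages 12 to 14 and small by 16 to 17. Weight bands are affected less than height in boys (25%) and about equally in girls (14%). BMI bands are little affected.

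The result is noise in a descriptive table. The false moves run almost equally up and down, nearly all to the neighbouring band, and nothing in the documents suggests that they favour one dose. A small real effect would be blurred rather than created. No test or dose decision rests on these tables. The rates also assume constant true z and linear interpolation between the SAP's rows; other interpolation methods changed them by less than one percentage point.

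**What to change.** In SAP 6.3.2, look up L, M and S at age in months at each visit. If only whole-year age is held, use Baseline whole-year age + 0.5 year + time since Baseline, and interpolate between the printed rows. For example, a boy recorded as 13 at Baseline is 13.5 + 112/365.25 = 13.81 at Week 16, so M = 160.35 + 0.307 × (167.46 − 160.35) = 162.53 cm. Use the same ages for the height percentile in 6.3.3. As a clarification, state that percentiles at age 18 or over are missing unless a chart row is added, and show the number at each visit.

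No new measurement is needed. The cost is an SAP addendum or programming note and modest reprogramming, in a plan whose version 3.0 was issued with database lock in view. The documents do not say whether date of birth is available. If it is not, the fallback works well at Week 16 but leaves about 17% of boys and 10% of girls changing height band at Week 124, against 35% and 14% under the current rule.

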6.3.2.3 Growth chart for weight by age and sex

In the Growth Chart for Weight, the L, M, and S parameters for each age in years were mapped to the chart values corresponding to the half-year time point for that year, with respect to sex.

Table 6–8: Growth Chart for Weight¹ (kg) by Age and Sex

Sex	Age (years)	Month in the chart	L	M	S
Male	12	150.5	-0.76027	43.18828	0.197464
Male	13	162.5	-0.65414	48.51113	0.194344
Male	14	174.5	-0.63492	53.91261	0.186442
Male	15	186.5	-0.72322	58.90293	0.176887
Male	16	198.5	-0.89044	63.03228	0.168655
Male	17	210.5	-1.0354	66.10749	0.163439
Female	12	150.5	-0.85031	43.96612	0.200419
Female	13	162.5	-1.00305	47.83661	0.19333
Female	14	174.5	-1.23801	50.92541	0.183328
Female	15	186.5	-1.51816	53.13327	0.172761
Female	16	198.5	-1.76224	54.61224	0.164368

Female	17	210.5	-1.86898	55.70624	0.160423
--------	----	-------	----------	----------	----------

¹ Centers for Disease Control and Prevention (2009). https://www.cdc.gov/growthcharts/percentile_data_files.htm

6.3.3 Blood pressure 99th percentile values by age, sex and height percentile

The Blood Pressure 99th Percentile Values table presents the values of the 99th percentile of systolic and diastolic blood pressure, by sex, age, and height percentile, for participants with age ≤17 years. Height percentile is calculated as described in Section 6.3.1 and should be rounded up or down to the nearest percentile in Table 6–9.

Table 6–9: Blood Pressure 99th Percentile Values¹ (mmHg) by Age, Sex and Height Percentile.

Sex	Age (years)	Height percentile	99 th percentile Systolic BP (mmHg)	99 th percentile Diastolic BP (mmHg)
Male	12	5	126	86
Male	12	10	127	87
Male	12	25	129	88
Male	12	50	131	89
Male	12	75	133	90
Male	12	90	134	90
Male	12	95	135	91
Male	13	5	128	87
Male	13	10	130	87
Male	13	25	131	88
Male	13	50	133	89
Male	13	75	135	90
Male	13	90	136	91
Male	13	95	137	91
Male	14	5	131	87
Male	14	10	132	88
Male	14	25	134	89
Male	14	50	136	90
Male	14	75	138	91
Male	14	90	139	92
Male	14	95	140	92
Male	15	5	134	88

Table 6–9: Blood Pressure 99th Percentile Values¹ (mmHg) by Age, Sex and Height Percentile.

Sex	Age (years)	Height percentile	99 th percentile Systolic BP (mmHg)	99 th percentile Diastolic BP (mmHg)
Male	15	10	135	89
Male	15	25	136	90
Male	15	50	138	91
Male	15	75	140	92
Male	15	90	142	93
Male	15	95	142	93
Male	16	5	136	90
Male	16	10	137	90
Male	16	25	139	91
Male	16	50	141	92
Male	16	75	143	93
Male	16	90	144	94
Male	16	95	145	94
Male	17	5	139	92
Male	17	10	140	93
Male	17	25	141	93
Male	17	50	143	94
Male	17	75	145	95
Male	17	90	146	96
Male	17	95	147	97
Female	12	5	127	86
Female	12	10	127	86
Female	12	25	128	87
Female	12	50	130	88
Female	12	75	131	88
Female	12	90	132	89
Female	12	95	133	90
Female	13	5	128	87
Female	13	10	129	87

Table 6–9: Blood Pressure 99th Percentile Values¹ (mmHg) by Age, Sex and Height Percentile.

Sex	Age (years)	Height percentile	99 th percentile Systolic BP (mmHg)	99 th percentile Diastolic BP (mmHg)
Female	13	25	130	88
Female	13	50	132	89
Female	13	75	133	89
Female	13	90	134	90
Female	13	95	135	91
Female	14	5	130	88
Female	14	10	131	88
Female	14	25	132	89
Female	14	50	133	90
Female	14	75	135	90
Female	14	90	136	91
Female	14	95	136	92
Female	15	5	131	89
Female	15	10	132	89
Female	15	25	133	90
Female	15	50	134	91
Female	15	75	136	91
Female	15	90	137	92
Female	15	95	138	93
Female	16	5	132	90
Female	16	10	133	90
Female	16	25	134	90
Female	16	50	135	91
Female	16	75	137	92
Female	16	90	138	93
Female	16	95	139	93
Female	17	5	133	90
Female	17	10	133	90
Female	17	25	134	91

Table 6–9: Blood Pressure 99th Percentile Values¹ (mmHg) by Age, Sex and Height Percentile.

Sex	Age (years)	Height percentile	99 th percentile Systolic BP (mmHg)	99 th percentile Diastolic BP (mmHg)
Female	17	50	136	91
Female	17	75	137	92
Female	17	90	138	93
Female	17	95	139	93

¹ US Department of Health and Human Services. “Diagnosis, evaluation, and treatment of high blood pressure in children and adolescents.” (2005).

6.4 Appendix 4: Details on amendments to the statistical analysis plan

6.4.1 Amendment 2

This statistical analysis plan has been amended to remove the COVID-19 TEAE and COVID-19 efficacy analyses, correct the PK and immunogenicity analyses, and clarify the missing data handling methods. In addition, other clarifications such as sections for safety topics of interest and safety topics closely monitored, and generic changes (eg. formatting or typos) have been incorporated.

Section # and Name	Description of Change	Brief Rationale
Global	Updated links to sections	Clarification
	Removed all COVID-19 specific analyses except “A summary of study visits impacted by the COVID-19 pandemic, and associated listing”.	Due to a sparsity of visits impacted with COVID-19, these analyses were removed.
	Correction of spelling, grammar, minor editorial, and typographical errors	Correction
1.2 Study Design	Removed “If Dose A is administered by a caregiver or a participant at home, the visit will be conducted via a telehealth system.”	Clarification; telehealth system will no longer be used.
4.1 Analysis Sets	Added that “Immunogenicity analyses will be based on SS or OLS, and participants will be summarized as randomized.”	Clarification
	Removed “Immunogenicity analyses will be based on the SS and as treated.”	Correction
	Added that Pharmacokinetic variables will be summarized as randomized.	Clarification
	Added that: 
 • OLS analyses will be based on the SS and as treated. • For summaries using both PK-PPS and OLS, participants will be summarized as randomized. 	Clarification
	Removed COVID-19 Free Set.	Correction
5.1 General Considerations	Clarified that for efficacy, SFU is excluded from by-visit tables but included in listings. Clarified that for safety, SFU is included in by-visit tables for the OLE and All Periods summaries only (not ITP).	Clarification
	From second bulleted paragraph, clarified that if at least one dose group has a value missing, missing categories will be created in the summaries of demographics and baseline characteristics.	Clarification

	From fourth bulleted paragraph, updated link to Section for imputing partial AE dates.	Clarification
	From fifth bulleted paragraph, clarified CDLQI endpoint as “Change from Baseline in CDLQI response” and fixed a typo in CIs.	Clarification
	Added rounding of AVAL, CHG and PCHG to the 12 th decimal place in order to avoid inaccurate floating-point representation of numeric values. Added that 95% CIs cannot be below 0 or exceed 100.	Addition
5.1.1.1.3 Study Periods	Clarified that any assessment or measurement made prior to or on the Week 20 visit will be attributed to ITP regardless of time of collection, and adverse events related to dosing and IMP administration will be attributed to the OLE period.	Clarification
5.1.1.3 Treatment assignment and treatment groups (and all applicable sections thereafter)	Clarified that dose groups refer to Dose A and Dose B, whereas weight-categorized dose groups refer to dose group specific breakdowns: 
 • Dose A (320mg Q4W), Dose A (160mg Q4W), Dose A (all) • Dose B (64mg Q4W), Dose B (32mg Q4W), Dose B (all) 	Clarification
	Clarified that for PK and immunogenicity analyses, all participants will be summarized according to Baseline weight-categorized dose group regardless of dose switching.	
5.1.1.7.4 Safety missing data	Separated this section’s language from Section 5.1.1.7.5.	Clarification
	Clarified that a complete date must be established for TEAEs for safety endpoints, and algorithms for start and stop date imputation have been described in Section 5.1.1.7.5.	Clarification

	Added that if the intensity of an adverse event is unknown, it will be considered as severe. If the relationship to study drug is missing, it is considered as related.	Addition
	Clarified that if the seriousness of an AE is unknown, no imputation will be made.	Clarification
	Clarified that vital signs, physical examinations, growth assessments, laboratory analyses will not be imputed and will be based on descriptive statistics only (observed case).	Clarification
5.1.1.7.5 Missing dates and times	Clarified language around assigning AEs and concomitant medications to ITP, OLE or both.	Correction
5.4.1.1.1 PASI response 5.4.1.1.2 IGA response 5.5.4 Scalp IGA response over time	Removed “electronically” from Investigator’s assessment.	Clarification
5.4.1.3 Sensitivity Analysis	Removed separate analysis on missingness of secondary endpoint data.	Correction
	Removed separate analysis on endpoints collected by different modalities, including data collected remotely vs. in-person.	
5.5.5 CDLQI (total score) change from baseline over time	Removed compliance analyses of CDLQI and by-visit analysis of CDLQI total score.	Correction
5.5.6 CDLQI 0/1 response over time	Replaced observed case with OC. Removed shift tables.	Correction
5.5.7 Efficacy and PK relationship	Removed specific language around efficacy-PK relationship analyses, and replaced with “An analysis, based on the Initial Treatment Period, will be conducted to investigate the relationship between plasma bimekizumab exposure and the efficacy variables (PASI response, PASI75, PASI90, IGA 0/1). This analysis will be described in a separate analysis plan and reported separately.”	Correction; specific analyses for efficacy-PK relationship will be reported in a separate analysis plan and are not appropriate in this SAP.

5.6 Safety Analysis	Clarified that SFU is not included in by-visit safety tables for the ITP alone, because few participants will not enter the OLE.	Clarification
5.6.1.1 Initial Treatment Period	Simplified algorithms to derive duration of exposure for ITP.	Clarification
5.6.1.2 Open Label Extension (OLE) Period	Removed the language around causing issues for attribution of AEs to doses occurring in the gap.	Correction; exposure should not be used for attributing AEs to periods. Time at risk is the relevant calculation.
5.6.2 Adverse Events	Clarified that on the AE on the date of a dose switch or on the Week 20 dose date, the AE will be attributed to the original dose/period (the “preswitch” dose/period).	Clarification
	Clarified that both Safety Topics of Interest and Safety Topics Closely Monitored will be given special attention in analysis.	Clarification
5.6.2.1 General data considerations for AEs	In the fourth paragraph, corrected AEs to be listed-only when occurring >140 days after the last dose (not 141).	Correction
	In the last paragraph, clarified that EAIR should be calculated to the first occurrence of the AE within ITP, and similarly for OLE. For combined tables, EAIR should be to the first occurrence regardless of period. EAER should include all repeat occurrences within the period of interest.	Clarification
5.6.2. Adverse events data considerations	Clarified that AE tables will summarize weight-categorized Dose A groups and All Participants on one page, and then the subsequent page will contain weight-categorized Dose B groups and All Participants.	Clarification

	
Summary by system organ class (SOC), HLT, and preferred term (PT):
 
 Removed nonserious TEAEs Clarified that a combined table of safety topics of interest and safety topics closely monitored will be created. 
Summary by relationship, SOC, HLT, and PT:
 
 Removed serious TEAEs Removed nonserious TEAEs 
Removed the following from ordered and subset of AE summaries:
 
 Any TEAE by SOC and PT for above reporting threshold of 5% Related TEAEs by SOC and PT above reporting threshold of 5% TEAEs Identified as Safety Topics of Interest by SOC and PT 
Antibody Data:
 
 Added Incidence of TEAEs per 100 participant years by SOC, HLT, and PT and by time of onset relative to NAB status. Note: Only presented for combined Initial Treatment Period and OLE Period. 
The following AEs will be listed only, and not summarized in the overall AE table:
 
 Any TEAE with onset at Day 1 Any TEAE related to TB including latent TB and IGRA tests 
The following Plain Language Summaries have been added:
 
 Incidence of Drug-related TEAEs – Overview 	
Correction; changed safety outputs to be in-line with study objectives, added immunogenicity relevant outputs, and added Plain Language Summaries required by Disclosures.

--	---	---

	
 Incidence of Drug-related TEAEs by Preferred Term Incidence of Serious Drug-related TEAEs by Preferred Term 	
5.6.2.3 Safety topics of interest (and all applicable sub-sections)	Clarified that TEAEs of safety topics of interest and safety topics closely monitored will be presented in a combined table for ITP, OLE, and All Periods.	Clarification
5.6.2.3.1 Infections (serious, opportunistic, fungal and TB)	Clarified that opportunistic infections will be identified using the SMQ “Opportunistic Infections (SMQ)” and that all TEAEs which code to a PT included in the Scope = Narrow search will be included.	Clarification
	Added a by-participant listing of “All Treatment-Emergent Adverse Events Related to TB including latent TB and IGRA tests”.	Addition
5.6.2.3.2 IBD	
Clarified that the combined table will present definite IBD (event type codes 3, 6, 9, 13, and 16) and probable IBD (event type codes 2, 5, 8, 12, and 15).
 
In the second paragraph after the bulleted list, clarified that incidence and event rate of adjudicated gastrointestinal events will be presented.
	Clarification
5.6.2.3.3 Injection site reactions	Moved the bulleted list of neutropenia events to the standalone Section 5.6.2.4.6.	Clarification
5.6.2.4 Safety topics closely monitored	Clarified that TEAEs of safety topics of interest and safety topics closely monitored will be presented in a combined table for ITP, OLE, and All Periods.	Clarification
	Added that, in this combined table, participant incidence, number of events, and exposure adjusted rates (incidence and event rate per 100 participant years) will be reported by SOC, HLT, and PT.	Addition

5.6.2.4.1 Hypersensitivity (including anaphylaxis)	Clarified that the combined table will include acute anaphylactic events (reported on the same day as when an injection was administered or 1 day after).	Clarification
	Removed AE glossary table, and any mention of standalone tables for hypersensitivity.	Correction; glossary was removed for Hypersensitivity due to sparsity of events.
5.6.2.4.2 Suicidal Ideation and Behaviour (SIB)	Clarified in the second paragraph that the combined table of safety topics of interest and safety topics closely monitored will include only the events adjudicated as suicidal by the committee.	Clarification
	Clarified that a stand-alone SIB table will present the incidence and event rate of adjudicated neuropsychiatric events by type.	
5.6.2.4.3 Cardiovascular events	Removed “potential” from potential cardiovascular events. Revised this section to correctly capture SMOs for cardiovascular events.	Correction; in line with updated algorithms .
5.6.2.4.5 Malignancies	Revised this section to use the correct strategy for capturing malignancies. The first incidence row will summarize “Any Malignancy” and the second row will summarize “Any Malignancy excluding melanomic skin cancers HLT”.	Correction; in line with updated algorithms .
5.6.2.4.6 Neutropenia	Created this section by moving the bulleted list of neutropenia events from Section 5.6.2.3.3 to this section.	Addition
5.6.3.1.1 Laboratory values over time	Corrected the criteria for potential drug induced liver injury (PDILI) summaries to use “>=” instead of “>” for ALT, AST, and Total Bilirubin.	Correction
5.6.3.3 Columbia suicide severity rating scale (C-SSRS)	Added a listing of all participants reporting at least 1 suicidal ideation or behavior.	Addition
5.6.3.6.3 Assessment and management of TB and TB risk factors	Added a listing of “All TEAEs related to TB including latent TB and IGRA tests”, with a relevant link to Section 5.6.2.3.1.	Addition

5.7.1.1 Pharmacokinetics	
In the first paragraph, added language that summaries will be created for ITP using PK-PPS and All Periods using OLS and PK-PPS combined.
 
In the second paragraph, added that a summary of bimekizumab plasma concentration over time will be reproduced to 1 decimal place for the Plain Language Summaries. Also added that that bimekizumab plasma concentration over time summaries will be repeated for anti-bimekizumab antibody status and by overall NAb status.
 
In the fourth paragraph, clarified that both by-visit summaries and figures of plasma concentrations will exclude data points with PDs expected to impact drug exposure.
 
In the bulleted list, out of window rules have been added to exclude pharmacokinetic samples based on their relative time to the current or previous dose.
	Addition and clarification
5.7.1.4 Immunological (Immunogenicity) Analysis	Added that Immunogenicity variables are the anti-bimekizumab antibody status, anti-bimekizumab antibody titer and neutralizing anti-bimekizumab antibody status derived from anti-drug antibody assays.	Addition
	Added that the samples will be titrated, and the ADA _b titer (reciprocal dilution factor, including the Minimum Required Dilution) will be reported.	
	Removed the definition of neutralizing assays.	Correction
	Added that the summary tables will be created for ITP using SS, and the All Periods using OLS.	Addition
5.7.1.4.1.1 ADA _b sample status	In the first bullet, added that ADA _b status can be confirmed regardless of availability of a titer value.	Addition

	In the second bullet, clarified that an ADAb status of negative can be confirmed where the bimekizumab concentration is less than or equal to the drug tolerance limit (200 µg/mL) of the validated ADAb assay.	Clarification
	Replaced ADAb level with “sample”. Removed language around anomalous values being excluded from summaries and being flagged by a pharmacokinetic expert.	Correction; values will be excluded as per PK-PPS.
5.7.1.4.1.2 Overall ADAb status	Clarified that overall ADAb status must also be summarized by Total for Dose A, Total for Dose B, and All Participants in addition to the weight-categorized dose groups.	Clarification
	Added to the bulleted list of ADAb status: 
 Overall ADAb status to Week 16 (SS) should be summarized by including and excluding baseline. Overall ADAb status to Week 20 (SS) should exclude baseline, and summarized by including and excluding SFU. Overall ADAb status to Week 124 (OLS) should exclude baseline and SFU. Overall ADAb status to SFU (OLS) should include all visits up (including and excluding Baseline) to SFU.	Addition; ADAb status summaries must be created for both the ITP (Week 16, Week 20) and OLS (Week 124).
5.7.1.4.1.3 ADAb Subcategories	Removed “pretreatment” from Category 1, 2, 5, 6, 8, 9.	Correction
	Clarified that categories will be derived for ITP (without OLE or SFU data), and for All Periods (with ITP, OLE, and SFU data).	Clarification

	
Added the following categories:
 
 • Total treatment-emergent (category 7 [categories 2 and 5 combined]): Includes study participants who are preADAb negative – treatment emergent ADAb positive (category 2) and preADAb positive – treatment boosted ADAb positive (category 5). • Total prevalence of preADAb positivity (category 8 [categories 3, 4, 5, and 6 combined]): Study participants that are tested ADAb positive at Baseline. • Missing (category 9): Includes participants who are antibody negative at Baseline, and have more than 1 post-treatment scheduled assessments reported as missing/inconclusive, while other samples are ADAb negative. Note this is also applicable to participants who have a missing Baseline sample, at least one missing/inconclusive postbaseline sample and have no ADAb positive samples. 	
Addition; ADAb categories 7, 8 and 9 have to be summarized.

5.7.1.4.1.4 Cumulative ADAb status groups for PK summaries	Clarified the derivation of ADAb status by period and up to the timepoint of interest.	Clarification
5.7.1.4.1.5 ADAb status groups for Efficacy Endpoint Summaries	Clarified that ADAb positive must exclude Baseline only (not SFU).	Clarification
	Clarified that ADAb negative can contain 1 post-baseline positive sample given all others are ADAb negative or missing/inconclusive.	Clarification
	Added that ADAb status for efficacy subgroups will be derived at Week 16 (excluding SFU) for the Initial	Addition; ADAb status for efficacy summaries must be created for both

	Treatment Period and Week 124 (including SFU) for the combined Initial Treatment and OLE Periods (OLS).	the ITP (Week 16) and OLS (Week 124).
5.7.1.4.1.6 Analysis	Added that analyses must be run on OLS, in addition to SS.	Addition
	
Clarified language around immunogenicity analyses.
 
In the first bullet, clarified that summaries of ADA_b status by periods of interest will be presented, along with the overall ADA_b status for efficacy endpoint summaries.
 
In the second bullet, clarified that the number and percentage of first ADA_b positivity (Category 7) participants will be summarized. Box plots of the titer will also be presented for time to first ADA_b positivity.
	Clarification
	The individual participant level ADA _b standalone listing was removed.	Correction; ADA _b values are presented in the PK listings, therefore standalone ADA _b listing was removed.
	
In the fourth bullet, clarified that PASI90 and IGA 0/1 responders (NRI) will be summarized by ADA_b titer (negative, titer <100 and titer tertiles > 100) and by dose group at Week 16 and Week 124. PASI75 and PASI100 will not be summarized.
 
In the fifth bullet, clarified that the number and percentage of PASI90 and IGA 0/1 responders will be summarized by overall ADA_b status. The data will be summarized graphically (NRI) and in a tabular format (NRI and OC). PASI75 and PASI100 will not be summarized.
	Clarification

	
In the sixth bullet, clarified that individual plots of BKZ concentration / ADAb titer will be based on PASI90 and IGA 0/1 (NRI). Plots will be grouped in the main ADAb categories, excluding category 7 and 8.
 
In the seventh bullet, clarified that the spaghetti plots will be for all ADAb positive participants (category 2 and 5).
 
Clarified the time at risk derivation for the TEAE tables by ADAb status, and the summarization of TEAEs prior to and after ADAb positivity.
	
5.7.1.4.2 Neutralizing anti-bimekizumab antibody	Clarified that NAb will be assessed using IL-17AA-specific and IL-17FF-specific assay methods.	Clarification
